Title: Parent/Nurse Controlled Analgesia in the Neonatal Intensive Care Unit

NCT Number: NCT01823497

Document Date Feb 7, 2013 (Date of IRB approval)

Methods

This single-center, prospective, RCT was approved by the hospital Institutional Review Board, and was registered at www.clinicaltrials.gov (ID: NCT01823497) by the principal investigator prior to study enrollment.

Setting

This study took place in the NICU at Children's Hospital of Wisconsin (CHW), with data collected between April 2013 and April 2015. At the time of the study, the unit consisted of a 43 bed intensive care unit and a 16 bed step-down unit with approximately 600 admissions per year.

Procedure

Potential participants were identified from the surgery schedule and the surgical team's work list that included any infant with a planned surgery. Initially, the study team also made contact with the mothers of potential participants in the hospital's Fetal Concerns Clinic. However, this recruitment method was unsuccessful, and was therefore discontinued.

Inclusion criteria: Infants 1) born no earlier than 34 weeks post menstrual age and having a corrected age no greater than 44 weeks at the time of enrollment, 2) having a birth or current weight of at least 2 kg, 3) undergoing an abdominal or thoracic surgical procedure conducted by the pediatric general and thoracic surgery team, and 4) expected to require opioids for at least 24 hours after the surgical procedure based on the opinion of the surgeon. Additionally, at least one parent was able to read and speak English. As recruitment proved more difficult than anticipated, the protocol was amended to remove the upper age limit, but the requirement of being cared for in the NICU remained.

Exclusion criteria: Infants 1) requiring vasopressors, 2) with significant prior opioid exposure (defined as > 2 days of continual exposure before surgery, or > 3 doses over the 5 days prior to the surgery), and 3) who were expected to be chemically paralyzed after surgery.

Design

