Enrolled patients who at any point prior to PNCA or COI discontinuation, subsequently required vasopressors, a high frequency oscillating ventilator, or benzodiazepines, acetaminophen or anti-inflammatory agents as adjuncts for pain were discontinued early from the study. At the time of the study, acetaminophen was not used as routinely as it is now. In order to not confound pain assessment and opioid consumption by having some patients receive it and others not, the study team chose to stop data collection if acetaminophen (or benzodiazepine) was administered. Data collection terminated for all other patients when the PNCA or COI was discontinued. However, patient orders were monitored for 5 additional days to assess whether methadone was started.

Independent variables were collected to describe the sample and to determine whether groups were equivalent on all potentially confounding variables. Demographic and anthropometric data were extracted from the electronic health record, and included gender, race, ethnicity, gestational age, weight at time of surgery, total time PNCA or COI was used, and whether the current surgery was the infant's first. We also recorded mechanical ventilation and

any unplanned re-intubation occurrences. PNCA injections and attempts, as well as COI boluses were recorded for day (0700-1859) and nighttime (1900 – 0659) shifts. Mothers were asked about perinatal use of antidepressant or illicit drugs.

Primary Outcome

Our primary outcome was opioid consumption, defined as the average amount of opioid consumed over the time on study, and reported in mg/kg/hr. For the PNCA group, it was calculated based on the number of hourly injections plus the basal rate. For the COI group, it was based on the infusion rate across the time on study and any boluses administered.

Secondary Outcomes

- 1) Average pain intensity over the time on study. Participant pain intensity was assessed using the Revised-Face, Legs, Activity, Cry, Consolability (Revised-FLACC) scale (Malviya, Voepel-Lewis, Burke, Merkel, & Tait, 2006), the scale currently used in our NICU for this patient population. The FLACC has been used previously for NICU infants (Ahn, Kang, & Shin, 2005), has been validated in numerous pediatric populations (McGrath et al., 2008), and was originally validated in children from 2 months – 7 years (Merkel, Voepel-Lewis, Shayevitz, & Malviya, 1997).

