- 2) Adverse events, defined a priori as naloxone rescue doses and any reintubation while on the opioid delivery system. Requiring methadone after the opioid delivery system was discontinued, was used as a measure of opioid tolerance. A modified Ramsey scale was used (Hoffman et al., 2002). Nurses reported sedation scores from 1 to 6, with 1 to 3 indicating significant sedation, 4 indicating asleep and easily arouseable or awake but drowsy, 5 indicating normal awake/alert, and 6 indicating anxiety and/or pain higher than baseline. Sedation scores below 4 were considered an indication of somnolence.

3) Parent and nurse satisfaction. No satisfaction tools in the extant literature would meet study requirements, therefore the investigators developed parent (Appendix A) and nurse (Appendix B) satisfaction surveys based on our previous studies (Czarnecki et al., 2017). Parents were asked about their satisfaction with 1) the pain management for their infant and 2) their involvement in the pain management for their infant. Parents in the PNCA group were also asked how often they pushed the PNCA button. Nurses were asked about 1) their satisfaction with the method of pain management for their patient, 2) whether parents were present during their shift, 3) whether they provided education to parents, and if so, 4) how long it took to provide the education. Directions for both surveys were explained at the time of consent to parents, and to nurses during daily rounds. Additionally, the study team contacted nurses on “off shifts” by phone to remind them of the need to complete the surveys. Printed blank copies of the parent surveys were left in their infant’s NICU suite. Printed blank copies of the nurses survey were available in a 2-sided envelope in the participant’s suite, with one side used to hold blank copies, and the other side clearly labeled for completed surveys (to protect anonymity). Parents were asked to complete the survey once a day, and nurses, once each shift. The research coordinator collected completed surveys daily.

Statistical Analysis and Data Management

Data were entered into a REDCap (<http://www.project-redcap.org>) database. Bimonthly reports were generated to look for missing data, outliers, and inconsistencies. Inconsistencies were checked against original data forms and corrections made as needed. CONSORT principles (Schulz, Altman, Moher, & Group, 2011) were used to assess recruitment success.

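### New vasopressor need, and high-frequency oscillating ventilation without reintubation, end participation but enter no defined safety outcome and no planned table by arm

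*Combined protocol and SAP*

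**What the plan says.** Three parts of the document bear on this.

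- **Entry.** The exclusion criteria under Procedure rule out infants "requiring vasopressors", so a later need for them is new since entry.
- **Stopping.** Protocol Details applies to "Enrolled patients who at any point prior to PNCA or COI discontinuation" meet one of the listed triggers: such infants "subsequently required vasopressors, a high frequency oscillating ventilator, or benzodiazepines, acetaminophen or anti-inflammatory agents as adjuncts for pain were discontinued early from the study".
- **Safety outcomes.** Secondary Outcomes item 2 reads: "Adverse events, defined a priori as naloxone rescue doses and any reintubation while on the opioid delivery system". Two further measures follow. For tolerance: "Requiring methadone after the opioid delivery system was discontinued, was used as a measure of opioid tolerance". For sedation: "Sedation scores below 4 were considered an indication of somnolence".

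The Statistical Analysis section reports adverse events as incidence pooled over postoperative days. It describes no breakdown of early discontinuations by reason and arm. The document contains no general definition of an adverse event or serious adverse event beyond these items.

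**The concern.** The plan treats a new need for circulatory support, or for oscillating ventilation, as important enough to end an infant's participation. It then gives that event no place in the safety results. An infant who starts vasopressors, with no naloxone and no reintubation, leaves the study with no adverse event recorded under the plan's definition.

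The two arms deliver morphine differently, so cardiorespiratory safety by arm is a fair question to ask of this trial. With only naloxone and reintubation counted, a statement that adverse events were rare or similar could be correct under the definition and still omit infants in one arm who left because their circulation or ventilation got worse.

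**Working it through.** **Inputs.** The triggers come from Protocol Details, the safety measures from Secondary Outcomes item 2, and the analysis set and reporting rule from Statistical Analysis and Data Management. The planned size of 30 per group (60 in total) comes from Sample Size/Power Analysis.

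**Step 1: the plan's own figure.** A two-sided t-test at 5% with a 0.74 SD difference and 80% power needs 29.7, so 30, per group by the noncentral t distribution. At 30 per group the power is 80.5%. The stated 30 reproduces. It serves the primary outcome only; nothing below depends on it except as a denominator.

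**Step 2: triggers against safety measures.**

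| Event before PNCA or COI ends | Ends participation? | In a defined safety outcome? |
|---|---|---|
| New vasopressor, no naloxone or reintubation | Yes | No |
| Oscillator, infant still intubated after surgery | Yes | No: there is no reintubation to count |
| Oscillator, infant already extubated | Yes | Yes: it entails reintubation, which counts if the delivery system is running |
| Any deterioration with naloxone or reintubation on the system | Depends on the trigger | Yes |

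The gap is the first two rows.

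**Step 3: could another part of the plan pick these up?**

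- Mechanical ventilation and unplanned reintubation are recorded, but among the variables used to describe the sample and check that groups are comparable. Ventilation is not a named outcome.
- The modified intent-to-treat set keeps a discontinued infant who received the allocated intervention and has at least one post-randomization outcome. That puts the infant in the denominator; it does not put the event in the numerator.
- CONSORT principles are cited for assessing recruitment success. No listing of discontinuation reasons by arm is promised.
- The explicit rule on data collection, "the study team chose to stop data collection if acetaminophen (or benzodiazepine) was administered", does not name vasopressors or the oscillator. What was still collected after those two triggers is unclear.

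**Step 4: possible size.** The documents give no rate, so these rates are assumed. With event rate p among 60 infants, the expected number is 60p and the chance of at least one is 1 − (1 − p)^60.

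| Assumed p | Expected events | Chance of at least one |
|---|---|---|
| 2% | 60 × 0.02 = 1.2 | 1 − 0.98^60 = 70% |
| 5% | 60 × 0.05 = 3 | 1 − 0.95^60 = 95% |
| 10% | 60 × 0.10 = 6 | 1 − 0.90^60 = 99.8% |

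Because the study stopped early, the actual denominator may be smaller, and these numbers with it.

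**Step 5: what a comparison by arm could show.** Take an invented split of 4/30 against 0/30 in the first two rows of the Step 2 table. The plan's adverse event rates from these infants would be 0% and 0%; counting the triggers gives 13.3% and 0%. The two-sided Fisher p is 2 × C(30,4)/C(60,4) = 2 × 27,405/487,635 = 0.11. The exact 95% intervals (Clopper-Pearson) are 3.8% to 30.7% for 4/30, and 0% to 1 − 0.025^(1/30) = 11.6% for 0/30. Even a split this uneven is not significant at the planned size, so the gain is disclosure rather than a test.

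**The case against.** The case against has real substance.

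- **Choice of events.** Naloxone and reintubation are opioid-related events, and choosing them is defensible in a small trial whose primary outcome is opioid consumption. This stands. It supports the two chosen events; it does not explain leaving reasons for discontinuation unreported.
- **Not every serious deterioration is missed.** A reader might infer that the gravest events appear in no safety outcome at all. The text does not support that. Deterioration with reintubation or naloxone on the system is counted, sedation scores recorded before discontinuation remain, and the documents do not grade severity.
- **Not necessarily on study morphine.** A reader might take every trigger to have arisen on study opioid. The stopping rule states an end to its window but no start. Infants were randomized after consent, which was sought before surgery, and the delivery system began on return to the NICU. As written, the window can include vasopressor use during surgery.
- **Background rate is not exposure.** A reader might point to the ordered background rates: 0.030 mg/kg/hr for COI against 0.010–0.0125 for PNCA, a ratio of 0.030/0.0125 = 2.4 to 0.030/0.010 = 3. Button doses add to the PNCA rate, nurse boluses add to the COI rate, and both arms share a maximum of 0.060 mg/kg/hr. Total consumption is what the trial set out to measure, so the ratio does not establish a difference in risk.
- **Randomization does not settle the comparison.** The trial is unblinded, with the acute pain service managing PNCA and the neonatology team managing COI. Starting these supports is a clinical judgement, and thresholds may differ by team.

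These points narrow the claim and limit how the counts may be read. None of them places a new vasopressor start, or oscillation in a still-intubated infant, in a reported safety result.

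**Conclusion.** The concern holds in a limited form, as a gap in safety reporting. Two kinds of event that end participation have no defined safety outcome and no planned table by arm: a new vasopressor need without naloxone or reintubation, and oscillation without reintubation. This follows from the text and rests on no assumed figure.

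Its size is unknown. The 1.2 to 6 expected events rest on assumed rates of 2% to 10% and on the planned 60 infants, and the 4/30 against 0/30 split is only an illustration. A reader might conclude that harm in one arm was hidden; the documents report no events of this kind and do not support that. What they support is that the planned safety summary could not show such a pattern if it occurred. The gap is worth closing because it bears on what that summary may claim, and the remedy is cheap.

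**What to change.** Change the reporting only; no clinical rule and no sample size is affected.

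1. In the safety summary, count infants with a first vasopressor use, and infants with a first oscillator use, after PNCA or COI was started. Give each by arm, over all infants who received the allocated treatment, with exact confidence intervals. Fisher's exact test may be added as a secondary description.
2. Tabulate all early discontinuations by reason and arm. List acetaminophen, anti-inflammatory and benzodiazepine stops separately by agent, and do not relabel them as pain failure or agitation: the reason Protocol Details gives for stopping data collection is confounding of pain assessment and opioid consumption.
3. Show triggers that occurred before the delivery system was started on their own line, since the stopping window has no stated start.
4. If this is added after data collection, label it post hoc.

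**Cost.** A few table rows. The team had to know the trigger to discontinue the infant, so no new data should be needed, although the start time relative to PNCA or COI may have to be looked up.

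**Downside.** Some events will reflect surgery or illness rather than morphine, the unblinded arms had different managing teams, and the counts will be too small for a firm test. The comparison should be presented as descriptive.

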Statistical analyses were calculated using SPSS 24 (IBM SPSS Inc., Chicago, IL) and SAS 9.4 software (SAS Institute Inc.). An unadjusted two-sided $P < .05$ was used for statistical

significance in all analyses. Unless otherwise noted, all analyses include data from post-operative days (POD) 0-3. All participants who received the allocated intervention, and had at least one post-randomized outcome were included in the modified intent-to-treat analyses. In addition, descriptive and frequency analyses were used to provide summary information about patient characteristics. We report the median (Mdn) with Interquartile range (IQR) throughout. A Wilcoxon signed rank test was used to compare paired data of day and nighttime injections and attempts for the PNCA group, and paired day and nighttime boluses for the COI group. A Mann Whitney test was used to compare PCNA and COI groups; comparisons based on categorical data were analyzed using Chi-square or Fischer's exact tests. We used a mixed model with random post-operative day (POD) to examine the associations between opioid consumption and considered covariates, which included race, gender, surgery location, gestational age, study group and POD. Covariance structure used was AR(1), model was estimated by using maximum likelihood, POD and intercept were modelled as random effects. To meet the normality assumption of the linear mixed model, the outcome opioid consumption was transformed by using logarithm at base 10. For model selection procedure, we first included one of the considered covariates in the model to examine any time-varying effects on the outcome (univariable model analysis), then repeated the same procedure for other covariates. Based on the univariable model analyses, any covariates and interaction terms with $P < 0.20$ were included in the final multivariable analysis. The final model only includes those covariates with $P < 0.05$. Adverse events are reported based on incidence collapsed across POD.

Sample Size/Power Analysis

Based on our retrospective study (Czarnecki et al., 2014), and using an estimate of a large effect size, we planned to include 30 patients in each group (60 patients total). This sample size

would have allowed for an 80% power at 5% significance level to use a t-test to detect opioid consumption differences between groups of at least 0.74 SD. The study was terminated early however, due to difficulty recruiting, time and cost constraints.

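### Device time, which arises after randomisation, is listed for checking group equivalence, while first surgery, listed as a potential confounder, has no route into the adjusted opioid model

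*Combined protocol and SAP*

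**What the plan says.** Protocol Details gives the purpose of the collected variables: "Independent variables were collected to describe the sample and to determine whether groups were equivalent on all potentially confounding variables". The list of data taken from the health record ends with "weight at time of surgery, total time PNCA or COI was used, and whether the current surgery was the infant's first". A separate sentence begins "We also recorded mechanical ventilation and" and goes on to "any unplanned re-intubation occurrences". The paragraph then covers injections, attempts and boluses, and maternal antidepressant or illicit drug use.

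Statistical Analysis and Data Management names the covariates considered for the mixed model of opioid consumption, "which included race, gender, surgery location, gestational age, study group and POD". Candidates are screened one at a time at P < 0.20, and only those with P < 0.05 stay in the final model. Groups are compared by Mann-Whitney, or by chi-square or Fisher tests for categorical data, at an unadjusted two-sided 5% level in all analyses. Descriptive and frequency summaries of patient characteristics are also planned. No equivalence margin is given, and no rule says what follows if the arms differ on a variable outside the candidate list.

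**The concern.** Three things do not fit together.

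- Time on the device is decided after assignment and may depend on the method or on the team managing it. A difference between arms would be a finding about the methods. Listing it among the variables on which the arms should be equivalent invites the reader to treat it as a nuisance.
- First surgery is fixed before randomisation, is collected, and falls under the plan's own description of potential confounders. It is neither a stratification factor nor a candidate covariate. If the arms differed on it by chance, the plan offers no adjustment.
- The plan sets out to determine equivalence, but the only between-group tools it describes are tests of difference, in a trial planned at 30 per arm and stopped early.

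At stake are the handling of a chance imbalance, some precision in a small trial, and the correct labelling of one result.

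**Working it through.** **1. The plan's own figure.** Inputs from Sample Size/Power Analysis: 30 per group, 0.74 SD, 5% level, t-test (taken as two-sided). The noncentrality is 0.74 × √(30/2) = 2.87 on 58 degrees of freedom. Power is 80.5%, the required size is 29.7, rounded up to 30 per group, and the smallest difference detectable with 80% power is 0.736 SD. The stated figure reproduces.

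**2. The two lists side by side.**

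| Variable in Protocol Details | When determined | Model candidate? | Other role in the plan |
|---|---|---|---|
| Gender | before randomisation | yes | stratification factor |
| Race, gestational age | before | yes | none |
| First surgery | before | no | none |
| Total time on PNCA or COI | after | no | none |
| Mechanical ventilation | timing not stated | no | none |
| Unplanned re-intubation | after | no | a priori adverse event |
| Maternal drug use | perinatal | no | none |

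Ethnicity and weight are also collected and are not candidates.

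**3. What a non-significant test would show.** For a yes/no factor with true proportions 20% v 40%, 30% v 50% or 40% v 60% (assumed), power at 30 per arm is 34-39% by the normal approximation and 26-30% by Fisher's test. An observed split of 10/30 against 17/30 (33% v 57%) gives P = 0.069 by chi-square and P = 0.119 by Fisher. For a continuous variable, the largest non-significant imbalance is t(0.975, 58) × √(2/30) = 2.002 × 0.258 = 0.52 SD.

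**4. What imbalance to expect.** Under randomisation the expected absolute imbalance is √(2/30) × √(2/π) = 0.258 × 0.798 = 0.21 SD. The shift in the opioid difference is the imbalance times the within-arm correlation with consumption. If first surgery explains 5-10% of variance (assumed), the correlation is √0.05 to √0.10, or 0.22 to 0.32.

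- Expected case: 0.206 × 0.22 to 0.32 gives 0.05-0.07 SD, about 6-9% of 0.74 SD.
- Edge of non-significance: 0.517 × 0.22 to 0.32 gives 0.12-0.16 SD, about 16-22% of 0.74 SD.
- With a correlation as high as 0.5 (assumed): 0.10 SD expected (14%) and 0.26 SD at the edge (35%).

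The final sample size is not given. At an assumed 15 per arm the expected imbalance is √(2/15) × 0.798 = 0.29 SD.

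**5. Precision.** Adjustment turns 0.74 SD into 0.74/√(1 − R²). At R² = 0.05 this is 0.759 SD and t-test power is 82.4%. At R² = 0.10 it is 0.780 SD and power is 84.4%. Both compare with 80.5% unadjusted. The calculation neglects the one degree of freedom spent.

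**The case against.** The strongest reply is that the plan never says baseline variables are tested, or that P > .05 will be called equivalence. The sentence on Mann-Whitney and chi-square tests names no baseline variable, and the plan assigns descriptive summaries to patient characteristics. Description is also the first purpose stated for collecting the variables. This stands: the testing is an inference from the word equivalent and from the absence of any other between-group method.

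A reader might infer that re-intubation is being treated as a confounder. The documents do not support that. Secondary Outcomes lists "Adverse events, defined a priori as naloxone rescue doses and any reintubation while on the opioid delivery system", and re-intubation sits outside the list that contains device time. The same paragraph goes on to "PNCA injections and attempts, as well as COI boluses were recorded for day (0700-1859) and nighttime" shifts. Those are arm-specific and cannot be balance variables, so the paragraph is a general account of data collection rather than a single equivalence list.

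A reader might also want ventilation at device start forced into the model. Parents were approached before surgery, the assignment was open, and the device was started on return to the NICU. Ventilation at that moment is therefore itself a post-randomisation measure, and the plan does not say when ventilation was recorded. Nor do the documents give grounds for removing race, or for excluding infants whose mothers reported drug use.

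Finally, 0.52 SD is not a typical imbalance. Randomisation exceeds it about 1 time in 20, and it applies to a continuous variable, whereas first surgery is yes/no.

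**Conclusion.** The point holds at minor severity. Device time is misplaced among comparability variables, and first surgery is collected as a potential confounder with no way into the adjusted model. The second statement takes the named candidates as the full list; no others are given.

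A reader might infer that the treatment comparison is biased. It is not: randomisation, stratified by gender and surgical location, prevents systematic confounding, and omitting a baseline covariate does not bias the comparison on average. Nor do the documents show device time being used as a confounder in analysis. It never enters the model, and the primary outcome is a rate in mg/kg/hr.

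The cost of leaving the plan as it is would be a chance shift, expected at about 6-9% of the 0.74 SD target, and about 2 to 4 points of power. Both figures assume that first surgery explains 5-10% of variance, which the documents neither give nor contradict. The power figures are for a single-measure t-test at the planned size. The actual model uses repeated post-operative days on log10 consumption, in a trial that stopped early, so they are only a guide.

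**What to change.** - Describe baseline variables by arm, without P values and without a claim of equivalence.
- Enter first surgery (yes/no) as a pre-specified fixed covariate in the adjusted opioid model, exempt from the 0.20 and 0.05 rules. Keep study group in the model on the same terms.
- Move total device time out of the comparability variables and report it by arm as an outcome. Say how it is counted for infants whose data collection stopped early. Re-intubation is already reported as an adverse event and needs no change.
- Adjust for ventilation only if status before randomisation is available; otherwise report it descriptively.

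The cost is SAP wording and one degree of freedom for first surgery. First surgery and device time are already collected; only the timing of the ventilation record needs checking.

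### Naloxone and reintubation are ascertained only until the PNCA or COI is discontinued, so events soon afterwards are not counted; the effect on the safety comparison is of unknown size and direction

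*Combined protocol and SAP*

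**What the plan says.** Item 2 under Secondary Outcomes gives the safety definition: "Adverse events, defined a priori as naloxone rescue doses and any reintubation while on the opioid delivery system". The same item also covers sedation scoring: "Sedation scores below 4 were considered an indication of somnolence". It treats a later need for methadone as a measure of tolerance.

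The Protocol Details section sets when observation ends. For infants who were not withdrawn early, "Data collection terminated for all other patients when the PNCA or COI was discontinued". The one activity described after that point has a single purpose: "patient orders were monitored for 5 additional days to assess whether methadone was started". Infants who needed vasopressors, oscillatory ventilation or certain adjunct drugs left the study before that point. For two of those drugs the section says outright that "the study team chose to stop data collection if acetaminophen (or benzodiazepine) was administered". The section also lists "any unplanned re-intubation occurrences" among the variables recorded, with no time window attached.

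Under Statistical Analysis and Data Management, "Unless otherwise noted, all analyses include data from post-operative days (POD) 0-3", and "Adverse events are reported based on incidence collapsed across POD".

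**The concern.** The observation window for both safety events closes at device discontinuation, and no later period is given for either. Opioid effect need not end when the pump does, so the window can be shorter than the exposure. If a device is stopped and naloxone or reintubation follows soon after, that event is not counted.

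Two consequences follow. First, recorded incidence can be too low, and a clean safety result could partly reflect where the window ends. Second, the loss need not be equal between arms. The trial is unblinded, the Acute Pain Service manages PNCA infants and the neonatology team manages COI infants. The timing of discontinuation relative to a safety event could therefore differ by arm for reasons unrelated to the true event rate.

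The primary outcome, opioid consumption, is not touched. What is at stake is the secondary safety comparison.

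**Working it through.** **1. The plan's own figure.** The documents give no number for adverse events. The only planning figure is 30 infants per group for a 0.74 SD difference in opioid consumption, at 80% power and two-sided 5% (Sample Size/Power Analysis). It reproduces:

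- Normal approximation: n = 2(1.960 + 0.842)² / 0.74² = 15.70 / 0.5476 = 28.7, so 29 per group.
- Exact t-test: n = 29.66, so 30 per group; power at 30 is 0.805.

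This has no bearing on the point except to supply the planned arm size used below.

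**2. The rules side by side.**

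| Item | Starts | Ends | Source |
|---|---|---|---|
| Reintubation as a safety event | device start | device off | Secondary Outcomes, item 2 |
| Naloxone as a safety event | device start | device off, by the definition or by the end of data collection | Secondary Outcomes, item 2; Protocol Details |
| Sedation scores | device start | end of data collection | Protocol Details |
| Methadone orders | device off | 5 days later | Protocol Details |
| Any of these in an infant discontinued early | device start | early discontinuation, possibly with the device still running | Protocol Details |

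No row extends naloxone or reintubation beyond device-off. The last row is a further gap: on-device safety events may go unseen in infants whose data collection stops early.

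**3. Can drug outlast the device?** The documents give no half-life. Assume 4 to 9 h. The fraction remaining is 2^(−t/half-life):

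- t = 2 h: 2^(−2/4) = 0.71 to 2^(−2/9) = 0.86.
- t = 24 h: 2^(−24/4) = 0.016 to 2^(−24/9) = 0.157.

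This supports only the premise that exposure continues after switch-off. Residual drug is not event risk, and the figures do not single out 24 h.

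**4. What a loss would do (assumed values).** Let p be the true event rate and f the share of events after switch-off. The recorded rate is q = p(1 − f), the expected count is 30q, and the chance of recording at least one event in an arm of 30 is 1 − (1 − q)^30.

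| p | f | q | Expected events in 30 | P(at least one recorded) |
|---|---|---|---|---|
| 5% | 0 | 5% | 1.5 | 78.5% |
| 5% | 0.25 | 3.75% | 1.13 | 68.2% |
| 5% | 0.5 | 2.5% | 0.75 | 53.2% |
| 10% | 0 | 10% | 3.0 | 95.8% |
| 10% | 0.25 | 7.5% | 2.25 | 90.4% |
| 10% | 0.5 | 5% | 1.5 | 78.5% |
| 20% | 0 | 20% | 6.0 | 99.9% |
| 20% | 0.25 | 15% | 4.5 | 99.2% |
| 20% | 0.5 | 10% | 3.0 | 95.8% |

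**5. Between arms.** If f is the same in both arms, a true risk difference is multiplied by (1 − f) and the risk ratio is unchanged. If f differs, a difference can appear where none exists. With p = 10% in both arms and f = 0.5 in one arm only, recorded rates are 10% and 5%, a spurious gap of 5 points. Either arm could be the one that loses events. Neither p nor f is in the documents, and f could be zero.

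**The case against.** **The sedation scores catch the episode.** A reader might infer that an over-sedated infant whose device is stopped leaves no trace in the safety results. The documents do not support that. Sedation is scored at least every 2 hours for the first 24 hours and at least every 4 hours after that, and scores below 4 are reported under the same outcome item. Somnolence before switch-off would normally appear there. This stands. It does not rescue the later naloxone dose or reintubation, which remains uncounted.

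**The naloxone wording is ambiguous.** The on-device qualifier may attach to reintubation alone. That is a fair reading, but naloxone collection then ends with data collection, at the same moment. Likewise, "any unplanned re-intubation occurrences" has no window of its own, but nothing carries it past the end of data collection, and the outcome definition would still exclude later events.

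**Discontinuation is not defined.** The documents give no reason, rule or frequency for stopping a device, and do not say whether a temporary hold counts as discontinuation. If a hold is still on-device time, an event minutes later is captured. This stands, and it limits how often the gap would matter.

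**Bias is not shown.** A reader might infer that the rule selectively removes opioid-related events and favours one arm. Separate unblinded teams make a differential loss possible. Nothing in the documents shows that one occurred, or in which direction.

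**One event in 30 is not the size of the problem.** At the planned arm size, 1/30 = 3.3 percentage points is the weight of a single event. It does not say how many are missed, and the study was terminated early, so the planned arm size may not be the achieved one.

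**Conclusion.** The point holds as a stated feature of the plan, not as missing detail. Reintubation, and naloxone at least through the end of data collection, are not ascertained after the PNCA or COI is discontinued, so an event shortly after switch-off is not counted. This can understate incidence. It could also distort the comparison between arms, by an unknown amount and in an unknown direction.

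The conclusion rests on two things: the plain reading of Protocol Details together with Secondary Outcomes item 2, and the assumption that opioid effect can persist after the pump stops. The rates in the working are assumed and show only what a given loss would do. The change is worth making because the safety comparison depends on few events and the extra ascertainment is cheap.

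**What to change.** Keep the a priori on-device outcome exactly as defined, including any reintubation and not only unplanned ones. Then add the following, identically in both arms:

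- Naloxone doses and any reintubation in a fixed period after discontinuation. A period of 24 h would serve as an example; it is not derived from the documents, and the choice should be stated and justified. Take naloxone from the order review already done for methadone, and reintubation from the health record.
- Separate lines for on-device events, post-device events and the total.
- A statement that this is an exception to the POD 0-3 window. Otherwise part of the added period is cut off for a device stopped late on POD 3.
- The same follow-up for infants discontinued early from the study, covering any remaining time on the device and the fixed period after it.
- A definition of discontinuation for ascertainment purposes, saying whether a temporary hold ends the on-device period.

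The cost is one more item in the order review and one record check per infant. Because data collection ran from April 2013 to April 2015, this would be a retrospective record review; if that is not possible, state the restriction as a limitation beside the safety results. The downside is that some late events may be unrelated to the study opioid, for example a new surgical problem or methadone started afterwards. The separate post-device line makes these visible.
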